6.1 Study Rationale

This study aims to understand the absorption, distribution, metabolism and elimination (ADME) of rencofilstat in humans further through the assessment of the mass balance recovery after a single oral dose of [¹⁴C]-rencofilstat. The routes and rates of elimination of [¹⁴C]-rencofilstat will be determined and whole blood, urine and faecal samples will be used for metabolic profiling and structural identification.

This is a single dose mass balance study of a single formulation, the study will be open-label and no randomisation is required.

6.2 Dose Rationale

The Phase I clinical study found that rencofilstat was safe and well tolerated at single doses from 75 mg to 525 mg and at multiple doses of 75 mg to 375 mg, administered daily for 28 days.

Systemic exposure of rencofilstat as measured by Cmax and AUC are approximately 10 to 100-fold above the drug's IC50 for inhibition of cyclophilins. Thus, the doses tested from the 75 mg dose upwards achieve systemic concentrations necessary to adequately engage the drug receptors at the site of action. Doses of 75 mg and 225 mg per day for 28 days were studied in the Phase 2 study in patients with NASH. A dose of 225 mg has been chosen for this study as in previous clinical studies, rencofilstat systemic exposure has been found to plateau at doses equal to and higher than 225 mg. It is expected that 225 mg will be the most efficacious dose and is currently the highest dose being evaluated in the Phase II clinical trials.

The dose of radioactivity has been determined following review of human dosimetry calculations provided by UK Health Security Agency. The associated radiation exposure will fall within International Commission on Radiological Protection (ICRP) (1992) Guidelines for Category IIb studies (1 to 10 mSv). The dose of radioactivity will be no more than 6.4 MBq.

To ensure that the [¹⁴C] drug product does not exceed the limit for radioactive dose approved by the Administration of Radioactive Substances Advisory Committee (ARSAC), the target specific activity of the drug substance will be set at 90% of 90% of the threshold radioactive dosing limit. This will allow for tolerances in the manufacturing processes for both drug substance and drug product thereby providing continued assurance for compliance with the ARSAC-approved limit for drug product radioactivity dose.

6.3 **Population Rationale**

As this is a Phase I study assessing the ADME, PK and safety of rencofilstat, the most relevant population is healthy volunteers. Subjects who are non-smokers without a history of alcohol or drug abuse or regular co-medication are proposed to avoid interaction on drug metabolism and to avoid non-compliance.

Data is not currently available from fertility and teratology studies with rencofilstat and subjects will be exposed to radiation; therefore, female subjects will not be enrolled in this study.

We acknowledge the ARSAC Notes for Guidance recommend that wherever possible, healthy subjects selected for research projects should be aged over 50 years [12]. However, the current study is designed to generate data for supporting the investigation of the human ADME of a drug, as well as generating samples for metabolite profiling and structural identification.

There are two main reasons for generating these data within a clinical development programme. The first is to provide human metabolite data that can be used to interpret the metabolism profiles seen in the preclinical species employed in the longer-term toxicity studies, to ensure that there is adequate toxicology coverage for the safe development of the drug in patients. The second is to provide data to understand how the drug is processed in physiologically normal subjects, because understanding the routes of metabolism and elimination in a healthy population generates the appropriate data to guide the clinical pharmacology package required to fulfil the regulatory requirements of a New Drug Application.

In order to address these two main aims of an ADME study, investigation of the drug under development is required in a population with normal physiological function, as it is recognised that certain physiological processes eg renal function, deteriorate with age and therefore it is preferable to use as healthy a population as possible, to mitigate against factors which may make interpretation of the data difficult. Also, healthy subjects as a trial population are ideal since they have a relatively stable physiological, biochemical and hormonal status, which removes any disease-related variations and variations due to concomitant medications. Therefore, given the aims of this ADME study our target age range for this study will be 30 to 65 years.

In addition, the initial target indication of this drug is NASH and, therefore, the target age range for the indication is included in the proposed age range for the study.

6.4 Risks and Benefits

6.4.1 Risks Associated with Rencofilstat Administration

Rencofilstat, previously known as CRV431, has been studied in three Phase I studies in healthy volunteers (CRV431-101, CRV431-103, and CRV431-104) as well as in a Phase 2a study in NASH patients (CRV431-201). CRV431-101 was a first in human study of rencofilstat comprised of 1) a SAD study; 2) a DDI study between rencofilstat and TDF; and 3) a 28-day MAD study. There were no deaths or SAEs in any parts of the study.

In Part 1, 20 AEs were experienced by 14 (47%) subjects following active treatment. The investigator assessed 18 events to be Grade 1, and 2 events to be Grade 2 in severity; 9 events were possibly related to study treatment, and 11 events were assessed as unrelated to the study treatment. Mild constipation was the most commonly reported AE, by 3 (10%) active treatment subjects, with 1 subject each in the 375 mg, 525 mg, and 375 mg (SMEDD ingested immediately following dilution) cohorts reporting 1 event each and was considered by the PI to be possibly related to the study.

In Part 2 headache was the most reported AE, reported 11 times by 8 subjects (44%). Fatigue and oropharyngeal pain were reported 3 times by 3 subjects (17%); dyspepsia, myalgia, nausea, and dizziness were reported 2 times by 2 subjects (11%). Events were generally distributed across treatment conditions, with a moderate increase seen in AEs in the combination rencofilstat plus TDF treatment (12/18 subjects [67%]) than in rencofilstat (8/18 [44%]) or TDF (7/18 [39%]) alone.

In Part 3, 2 subjects were discontinued due to AEs (1 due to urinary tract and yeast infections and 1 due to headache and lower abdominal pain). Only 3 AEs occurred in \geq 3 subjects: headache in 4 subjects (12%); fatigue, and diarrhoea in 3 subjects (9%). All events were Grade 1 or 2 in severity. There was no apparent relationship between rencofilstat dose level and AE frequency.

Overall, there was no trend observed for AE reporting in relation to rencofilstat dose. There were no remarkable observations in the remaining safety assessments for vital signs, 12-lead ECGs, or safety laboratory measurements in this study.

In study CRV431-103, there were no SAEs or deaths reported following treatment with 75 mg rencofilstat alone or in combination with 400 mg ketoconazole or 2 mg midazolam. One patient discontinued study participation due to a TEAE of elevated ALT/AST and subsequent COVID-19 infection. Twenty-eight AEs were recorded for 12 subjects. Investigators assessed 21 AEs as Grade 1, 6 AEs as Grade 2, and 1 AE as Grade 3. The grade 3 AE, elevated ALT, was considered unrelated to study drug and instead related to COVID-19 infection. TEAEs reported in 2 or more subjects were nausea (4 subjects [14.8%], diarrhoea, dizziness, headache, alanine aminotransferase increased, and aspartate aminotransferase increased (2 subjects [7.4%]). There were no findings or changes from baseline observed in any of the laboratory parameters (haematology, coagulation, blood chemistry, urinalysis), vital signs, pulse oximetry or ECG that were deemed to be clinically significant by the investigator.

In study CRV431-104, there was 1 AE related to clinically significant out-of-range vital signs (blood pressure increased) reported by 1 subject in the fed cohort. The AE was Grade 1 (mild) and judged by the Investigator as not related to study treatment.

Overall, rencofilstat was safe and well tolerated at all combinations tested to date in healthy subjects. There are no important identified risks or potential identified risks from the rencofilstat development program.

Non-clinical genotoxicity studies were all negative. These data presented a favourable safety profile for rencofilstat with acceptable safety margins that support the proposed clinical development program. No reproductive or developmental toxicity studies of rencofilstat have been performed as of the IB cut-off date of 01 Oct 2022. However, no females will take part in this study, and the male volunteers must agree to adhere to the contraception requirements defined in Section 9.4. No phototoxicity studies have been conducted on rencofilstat as of the IB cut-off date of 01 Oct 2022. Owing to the unavailability of phototoxicity data, subjects will be advised to minimise exposure to sunlight following dosing until discharge from the study (see Section 9.6).

All formulation excipients are United States Pharmacopeia (USP) grade or National Formulary (NF) grade and therefore have a Generally Recognised As Safe (GRAS) designation. Consequently, it is deemed safe to use in this study.

Given the current safety results, the benefit-risk is anticipated to be favourable at all dose levels tested.

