8.1 Study Plan

This is a single centre, open-label, non-randomised, single period, single dose study in healthy male subjects designed to assess the mass balance recovery, PK, metabolite profile and metabolite identification of rencofilstat. It is planned to enrol a single cohort of 6 subjects.

All subjects will receive a single 225 mg oral dose of [¹⁴C]-rencofilstat, as a SMEDDS oral emulsion, containing NMT 6.4 MBq, in the fasted state.

Subjects will undergo preliminary screening procedures for the study at the screening visit (Day -28 to Day -2). Subjects will be admitted in the evening on the day before dosing (Day -1).

Whole blood, plasma, urine and faeces samples will be collected at regular intervals for PK analysis, TR analysis, metabolite profiling, mass balance and safety as applicable, from pre-dose to discharge from the clinical unit. Urine and faeces samples may be collected at return visits or home visits if mass balance criteria has not been met by a subject.

Subjects will be dosed on the morning of Day 1 following an overnight fast (minimum 8 h) and will remain resident in the clinical unit until up to 504 h after dosing (up to Day 22).

It is planned that subjects will be released as a group when all subjects have achieved a mass balance cumulative recovery of >90% or if <1% of the dose administered has been collected in urine and faeces within two separate, consecutive 24 h periods. This may result in the subjects being discharged as a group prior to completion of the planned residency period.

If the mass balance criteria are achieved during the planned residency period, collection of all samples (blood, urine and faeces) will be stopped once the current 24 h collection period is complete, and subjects will undergo discharge assessments.

If the mass balance criteria have not been met by all subjects on the morning of Day 22, the residency period for the subjects not achieving the mass balance criteria may be extended up to a maximum of 96 h (Day 26; 600 h post-dose). Only urine and/or faecal samples will be collected during the extended residency period.

If the mass balance criteria have not been met by all subjects on the morning of Day 26, subjects not achieving the release criteria may be required to make up to 2 return visits (each of 24 h duration) at (nominally) Day 28 (+2 days) and Day 35 (\pm 2 days) for additional collection of excreta samples (urine and/or faecal samples).

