9.6 Additional Study Restrictions

The following additional restrictions will be in place for the duration of the study:

- 1. Subjects must abstain from alcohol during the 24 h prior to screening and the 24 h prior to admission until discharge from the clinical unit
- 2. Subjects must not drink liquids or eat food containing grapefruit, cranberry, caffeine or other xanthines from 24 h prior to admission until discharge from the clinical unit
- 3. Subjects should refrain from eating food containing poppy seeds for 48 h prior to screening and for 48 h prior to admission until discharge from the clinical unit
- Subjects must not take part in any unaccustomed strenuous exercise from the 72 h before the screening visit and then from 72 h prior to admission until discharge from the study
- 5. Must not donate blood or plasma (outside of this study), from screening, throughout the study duration, and for at least 90 days following dose of IMP
- 6. Due to the unavailability of phototoxic data for rencofilstat, subjects will be advised to minimise exposure to sunlight by spending a reduced amount of time outdoors/remaining inside the clinical unit during the residential periods of the study, wearing sunglasses and clothing that minimises exposure to sunlight and using sun cream on exposed areas when going outdoors. They will also be advised not to use sunbeds. This restriction will be advised from dosing until 7 days post-dose

7. Subjects will not be permitted to shower for 24 h post-dose (to ensure the collection of all samples)

The additional restrictions above are not exclusion criteria; if non-compliance occurs, a protocol deviation will be completed.

10 Study Procedures

Study procedures will be performed as detailed in the study schedule of assessments in Appendix 2, and in accordance with Quotient's standard operating procedures (SOP)s unless otherwise stated in this protocol.

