10.3.4 Return Visits

If the mass balance criteria have not been met by the morning of Day 26, subjects not achieving the release criteria may be required to return to the clinical unit for up to 2 return visits on Day 28 (+2 days; 648 h post-dose) and (if mass balance criteria are still not met by Day 28) Day 35 (±2 days; 816 h post-dose) for 24-h faeces and/or urine collections as described in Appendix 2.

Refer to Section 8.1 for further details.

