18.5 Declaration of the End of the Study

The end of the study is defined as the last visit of the last subject (eg discharge from the study). Any changes to this definition will be notified as a substantial amendment (see Section 17.1).

The EC and MHRA should be notified of the conclusion of the study within 90 days of the end of the study, or within 15 days if the study is terminated early, clearly explaining the reasons for the termination.

The ARSAC Practitioner will also be notified of the end of trial or early termination of the trial within an appropriate timeframe.

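### Protocol Section 6.4.1 promises sun-avoidance advice until discharge from the study, but Section 9.6 item 6 ends it 7 days after dosing, 14 days before the planned Day 22 discharge

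*Protocol*

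**What the plan says.** Two sections of the current protocol (Version 3.0) give the same precaution for the same reason, the lack of phototoxicity data, but end it at different times.

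- Section 6.4.1 (risks of rencofilstat): "subjects will be advised to minimise exposure to sunlight following dosing until discharge from the study (see Section 9.6".
- Section 9.6 item 6 (additional restrictions): "This restriction will be advised from dosing until 7 days post-dose". The same item foresees subjects leaving the building, since it advises "using sun cream on exposed areas when going outdoors".

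The timing of discharge comes from four other places.

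- Section 8.1: subjects "will remain resident in the clinical unit until up to 504 h after dosing (up to Day 22"), with earlier group release possible once all of them meet the mass balance criteria.
- Section 8.1: for subjects who miss the criteria, residency may be "extended up to a maximum of 96 h (Day 26; 600 h post-dose"). After that, "subjects not achieving the release criteria may be required to make up to 2 return visits (each of 24 h duration").
- Section 10.3.4: the Day 35 visit takes place "if mass balance criteria are still not met by Day 28".
- Section 18.5: "The end of the study is defined as the last visit of the last subject (eg discharge from the study"). This ties discharge from the study to the last visit, which for a recalled subject is later than leaving the clinical unit.

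**The concern.** Section 6.4.1 is where the protocol justifies exposing healthy volunteers, who gain no benefit, to a compound not tested for phototoxicity. It offers sun-avoidance advice as the mitigation and sends the reader to Section 9.6 for the detail. Section 9.6 then delivers a shorter period, so a site that follows it stops the advice at 7 days.

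Neither section gives a reason for 7 days, and nothing else in the protocol reconciles the two end points. By contrast, the contraception period in Section 9.4 is derived explicitly from the half-life.

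There is also a small consequence for conduct. Section 9.6 closes by saying that non-compliance with its restrictions is recorded as a protocol deviation. After 7 days, the same behaviour would be a deviation under the Section 6.4.1 period but not under item 6.

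**Working it through.** **Inputs.** Dosing is at 0 h on Day 1. Item 6 of Section 9.6 ends the advice at 7 days. Planned discharge is 504 h (Day 22) and extended discharge 600 h (Day 26), both from Section 8.1. Return visits start at 648 h (Day 28, +2 days) and 816 h (Day 35, ±2 days), from Section 10.3.4. Each visit lasts 24 h (Section 8.1).

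**Reproducing the protocol's own day numbers** (study day = hours/24 + 1):

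- 504/24 + 1 = Day 22
- 600/24 + 1 = Day 26
- 648/24 + 1 = Day 28
- 816/24 + 1 = Day 35

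All four agree with the protocol.

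**End of advice under Section 9.6:** 7 × 24 = 168 h, which is Day 8.

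**Gap between the two end points** = (discharge time − 168)/24 days. For a recalled subject, discharge is taken as the visit start plus 24 h. Non-resident days are those between 600 h and the last visit's start, less one day for the Day 28 visit where a Day 35 visit follows.

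| Discharge scenario | Discharge (h) | Gap (days) | Non-resident days within the gap |
|---|---|---|---|
| Planned, Day 22 | 504 | (504 − 168)/24 = 14 | 0 |
| Extended, Day 26 | 600 | (600 − 168)/24 = 18 | 0 |
| After the Day 28 visit | 648 + 24 = 672 | (672 − 168)/24 = 21 | (648 − 600)/24 = 2 |
| Same, 2 days late | 720 | (720 − 168)/24 = 23 | (696 − 600)/24 = 4 |
| After both visits, Day 35 | 816 + 24 = 840 | (840 − 168)/24 = 28 | (816 − 600)/24 − 1 = 8 |
| Same, on Day 33 | 792 | (792 − 168)/24 = 26 | (768 − 600)/24 − 1 = 6 |
| Same, on Day 37 | 888 | (888 − 168)/24 = 30 | (864 − 600)/24 − 1 = 10 |

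When both visits are made, moving the Day 28 visit by up to 2 days does not change the non-resident total. Home collections after Day 35 have no stated end and are not counted. If the group were released before 168 h the gap would reverse, because Section 9.6 would then run longer than Section 6.4.1.

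**Context only.** Section 9.4 gives a mean half-life of 98.138 h at 225 mg. Assuming single-exponential decline, 168/98.138 = 1.7 half-lives, leaving about 31%, and 504/98.138 = 5.1 half-lives, leaving about 3%. This says nothing about whether 7 days is safe. It shows only that 7 days cannot be taken as an obvious washout point.

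**The case against.** The strongest reply is that the site has one executable instruction. Section 6.4.1 is narrative and defers to Section 9.6, whose items each set their own end point. On that view Section 6.4.1 is just an inaccurate summary. The measure is also only advice, the study is a single dose in six subjects, no endpoint is touched, and the planned gap falls entirely within residency. What subjects are actually told depends on the information sheet, which is not part of the documents reviewed.

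Much of this stands. The practical effect is small, and Section 9.6 is the text a site would follow. That is also why the mismatch matters: following it delivers less than the risk section relies on.

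The opening line of Section 9.6, which applies its restrictions throughout the study, leans towards the Section 6.4.1 period. It does not settle the intent, because items 5 and 7 also depart from it.

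Two further points are fair. Shortening Section 6.4.1 would be as consistent with the text as lengthening item 6. A rule tied to discharge from the study would also have no fixed end date for a subject on home collections, and would lengthen the period in which a lapse counts as a deviation. These bear on the choice of correction; neither removes the conflict.

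**Conclusion.** The inconsistency is real, and the text is wrong as written. The end points differ by 14 days at the planned Day 22 discharge and 18 days at Day 26, all of it while resident. For recalled subjects they differ by 21 to 23 days (2 to 4 non-resident) after Day 28 only, or about 28 days (26 to 30; about 8 non-resident, range 6 to 10) after Day 35.

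These figures assume that return visits start at the stated times, allowing for the windows, and that discharge follows the 24 h collection. For recalled subjects they also read discharge from the study as the last visit, following Section 18.5.

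The documents do not show which duration was intended. This is a correction that should be made to a safety instruction. It has no bearing on the statistical analysis.

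**What to change.** Replace the last sentence of Section 9.6 item 6 so that the advice runs *from dosing until discharge from the study, and for at least 7 days post-dose*. Use the same wording in Section 6.4.1, and align any subject-facing text that repeats the 7-day period. The 7-day minimum preserves the present advice if the group is released early.

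If the sponsor does intend 7 days, change Section 6.4.1 to 7 days instead and state the reason.

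The drafting cost is one sentence in Section 9.6 and a few matching words in Section 6.4.1, plus the information sheet if affected. The cost to subjects under the base plan is about 14 more days of sun-avoidance advice, all while resident. For a recalled subject it would also cover the non-resident days shown in the table, and any home-collection period that counts as part of the study.

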6.4.2 Risks Associated with Administration of Radioactivity

The dosage form will contain a radionuclide, not more than (NMT) 6.4 MBq ¹⁴C, so subjects will be exposed to ionising radiation. The effective dose that each subject will receive from 1 administration of 6.4 MBq ¹⁴C will not exceed 2.0 mSv. This is approximately 9 months of the average radiation exposure received in the UK each year (2.7 mSv; data obtained from UK Health Security Agency Ionising Radiation Exposure of the UK Population: 2010 Review [13]) and is slightly more (1.1 times) than the radiation dose that would result from 4 abdominal X-rays (0.47 mSv each). It is believed that any increase in the amount of radiation that is received above natural radiation carries a risk of later developing serious and possibly fatal conditions. The risk associated with the maximum possible dose of radiation in this study is very small indeed and is considered to be acceptable.

Extrapolation of data from epidemiological studies of cancers induced by radiation exposure indicates that the risk factor for an adult UK population of both sexes (age range 18 to 64) is 5×10^{-2} per Sv [14]. From this it can be estimated that the lifetime risk of inducing a fatal cancer in a healthy individual from the total exposure of 2.0 mSv is approximately 1 in 10,000. The lifetime risk for being diagnosed with cancer in the UK is around 1 in 2 [15], indicating that this additional risk from this amount of radiation exposure is minimal.

